2.1 Primary outcome and endpoint

The primary purpose of this study is to compare the patient's ability to ambulate on POD 1 in patients that have received 5, 10 or 20 ml local anesthetic injection for SSACNB. This will be evaluated by determining how quickly a patient is able to ambulate over 10 meters on POD 1 (10 meter walk test).

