The subject will be met in the preoperative area by a staff anesthesiologist, who interviews and examines the subject. A full explanation of the neuraxial anesthetic and adductor canal block, including risks, benefits and alternatives, will be given and informed consent for anesthetic services obtained. Quadriceps motor strength and adductor strength will be assessed prior to any nerve blockade. Muscle strength will be assessed with the kio Sensor (Kio Inc., Madison, WI USA). The kio sensor is a force monitoring device that provides objective measurements of patient strength (traditional measurements or Manual Muscle Testing typically relies on subjective assessments by medical staff). To assess the subject's quadriceps and adductor strength, the kio sensor will be attached to the subject's ankle or upper leg and subject will be asked to forcefully extend the leg at the knee or adduct their leg. The kio Sensor is not currently commercially available and is currently in the development stage (see attached Phase I progress report – APPENDIX D). A sensory exam of the leg (temperature and pinprick) will also

be conducted prior to nerve blockade to determine baseline sensation of femoral, obturator and lateral femoral cutaneous nerves. For these tests, the jagged edges of a broken tongue depressor and alcohol swab will be used to produce pinprick and cold sensation. Subjects will be asked to report if sensation is normal, absent or decreased to both pinprick and cold.

From the subject's medical record the SF12 mental component and physical component, WOMAC and Knee Society Score, UCLA activity score, preoperative range of motion and degree of varus/valgus deformity will be collected. These scores and procedures are standard of care for all patients undergoing a TKA.

Adductor Canal Block Procedure:

An intravenous catheter will be placed, the subject will be transported to the block room or another room appropriate for provision of regional anesthesia and the subject will be pre-medicated with midazolam and/or fentanyl as needed at the discretion of the staff anesthesiologist.

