Physical therapy will determine pain with physical therapy, quadriceps strength, passive flexion/extension range of motion, postoperative quadriceps strength, postoperative adductor strength, and 10 meter walk test (gait velocity) at 24 and 48 hours postoperatively. All measurements of strength will be done using the Kiiro Sensor. Based on physical therapy team experience, patients are currently able to ambulate 10 meters in approximately 45 seconds on postoperative day one with 20 ml of local anesthetic injected into the adductor canal. The physical therapy team feels that ambulation velocity is generally limited by weakness and pain. However, we do not currently know if decreasing the dose of local anesthetic injected into the adductor canal will result in improved ambulation resulting from increased strength or worsened ambulation performance secondary to increased pain.

Concomitant Medications:

Analgesic and anti-emetic requirements for block placement, intraoperatively, in PACU, at 24 hours, 48 hours and during course of hospitalization will be extracted from the patient's electronic medical record.

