7.2 Subject withdrawals

At any point prior to or during the intervention period, the subject's clinical care team or a study physician may decide the subject should be withdrawn from the study. If a subject is withdrawn from the study for any reason the subject will then be followed according to the standard of care follow-up plan.

Study intervention will immediately stop and subject's clinical care team and a study physician will be immediately notified if one of the following occurs:

- 1) The subject suffers a severe adverse perioperative outcome that precludes participation in physical therapy or measurements of motor strength or sensory examination

In the event the study method is terminated, the reason for termination will be documented on a case report form.

8. Data analysis and statistical considerations

All data will be summarized using standard descriptive statistics, including mean, standard deviation, minimum, maximum, median, inter-quartile range, and confidence intervals, as appropriate. The data will be presented graphically (where possible) using scatter plots, profile plots, or histograms. Data analyses will be performed on an intent-to-treat basis using SAS (SAS Institute Inc., Cary, NC; version 8.2 or greater) or Minitab (Quality Plaza, State College, PA; version 13.0 or greater). The primary analyses will consist of comparing the three study volumes of injection for superiority. For all tests, statistical significance will be defined as a p-value less than 0.05. ANOVA and two-sample t-test will be used to compare the data between the three groups or between any two individual groups. Repeated measures ANOVA will be used to analyze multiple follow-up data points. Patients with missing longitudinal data will be handled by either using data imputation methods to replace the missing data or via the use of repeated measures ANOVA to better approximate the average values at each time point. Bonferroni correction will be utilized to counteract the problem of [multiple comparisons](#) and control the [familywise error rate](#).

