8.1 Sample size determination

This study is a randomized, three group (5, 10, 20 ml bupivacaine), mixed study using the primary endpoint of ambulation or gait velocity over 10 meters (10 meter walk test) on POD 1. The data from this preliminary study will be used to generate hypotheses for future trials. We performed an effect size calculation based on the ratio of the hypothesized differences and the standard deviation based on our current experience. Based on physical therapy team experience, patients are currently able to ambulate 10 meters in approximately 45 seconds on postoperative day one with 20 ml of local anesthetic injected into the adductor canal. The physical therapy team feels that ambulation velocity is generally limited by weakness and pain. However, previous retrospective research done at our own institution demonstrated that adductor canal block patients were able to ambulate more effectively than those patients receiving a femoral nerve catheter (i.e. those with a more profound motor blockade). We therefore hypothesize that decreasing the dose of local anesthetic delivered into the adductor canal will decrease the amount of time required to ambulate 10 m and that this difference could approach 15 seconds. We hypothesize that the standard deviation may be of similar magnitude. With a power of 0.8 and significance level of 0.05, 16 patients are required per group. Increasing enrollment to 20 patients per group will allow for patient drop out.

9. Risks and benefits of trial participation

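### The primary walk analysis is valid but uses no baseline information; pre-specifying pre-block quadriceps strength as the one covariate would be a cheap gain in precision if it predicts walking

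*Combined protocol and SAP*

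**What the plan says.** The primary endpoint (section 2.1) is speed over 10 m on POD 1. Section 8 says that "The primary analyses will consist of comparing the three study volumes of injection for superiority" and that "ANOVA and two-sample t-test will be used to compare the data between the three groups or between any two individual groups". Repeated measures ANOVA is reserved for multiple follow-up points, and Bonferroni is named without a number of comparisons. No covariate, ANCOVA or stratification factor is mentioned anywhere.

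Section 7, under the pre-procedure activities, says: "Quadriceps motor strength and adductor strength will be assessed prior to any nerve blockade". The schedule of activities lists this assessment on the morning of surgery for all subjects. The volume is randomised later, once the needle is placed and aspiration is negative (section 7, study randomization). Section 2.2 lists preoperative quadriceps strength only among the variables to compare between groups. No preoperative 10 m walk is scheduled.

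On what drives walking, section 7 says, and section 8.1 repeats: "The physical therapy team feels that ambulation velocity is generally limited by weakness and pain". Section 8.1 hypothesises that, with a lower dose, "this difference could approach 15 seconds", with an SD of similar size, and concludes: "With a power of 0.8 and significance level of 0.05, 16 patients are required per group". Enrolment is raised to 20 per group to allow for dropout.

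**The concern.** The trial is small, and its sample size leaves little spare power, above all once Bonferroni is applied. Differences between patients in the strength they bring to surgery stay in the error term of the primary comparison. If that strength is related to POD 1 walk time, part of this error could be removed with a measurement the trial already takes. Because it precedes randomisation, the volume cannot affect it, and adjusting for it does not bias the comparison.

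Timing also matters. The plan will display preoperative strength by group but has no planned way of using it. Deciding to adjust after seeing an imbalance would be data-driven; naming the covariate in advance avoids that.

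**Working it through.** **Inputs.** From section 8.1: difference 15 s, SD about 15 s, alpha 0.05, power 0.8, 16 evaluable per group and 20 enrolled. Assumed: two-sided tests, equal SDs, a linear covariate effect, three Bonferroni pairs (0.05/3 each), and rho, the within-group correlation of pre-block quadriceps strength with POD 1 walk time. Only the size of rho matters. The documents do not give it, so a range from 0 to 0.5 is shown.

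**1. The plan's own figure.** n per group = 2 × (1.960 + 0.842)² × (15/15)² = 15.70, rounded up to 16. The stated 16 reproduces as an unadjusted two-sided comparison of two means.

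**2. Unadjusted pairwise power, error pooled over three groups, 16 per group.** Error df = 3 × 16 − 3 = 45. Noncentrality = (15/15) × √(16/2) = 2.828. From the noncentral t distribution, power is 79.0% at 0.05 (critical t 2.014) and 63.5% at 0.05/3 (critical t 2.487).

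**3. ANCOVA with one covariate.** Error df = 44. Residual variance is multiplied by 1 − rho². Estimating the slope inflates the variance of a contrast by about 1 + 1/(44 − 1) = 1.0233. The net factor is v = (1 − rho²) × 1.0233, and the noncentrality is 2.828/√v.

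| rho | v | noncentrality | power at 0.05 | power at 0.05/3 |
|---|---|---|---|---|
| unadjusted | 1 | 2.828 | 79.0% | 63.5% |
| 0 | 1.023 | 2.796 | 78.1% | 62.2% |
| 0.2 | 0.982 | 2.854 | 79.7% | 64.3% |
| 0.3 | 0.931 | 2.931 | 81.8% | 67.1% |
| 0.4 | 0.860 | 3.051 | 84.7% | 71.1% |
| 0.5 | 0.767 | 3.229 | 88.4% | 76.7% |

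**4. Break-even.** v = 1 when rho² = 1 − 1/1.0233 = 0.0227, so rho is about 0.15. Below that, adjustment costs slightly more than it returns.

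**5. If all 20 per group are evaluable.** At 0.05, power is 87.5% unadjusted and 89.8%, 91.9% and 94.5% at rho 0.3, 0.4 and 0.5. At 0.05/3 it is 75.4% unadjusted and 79.0%, 82.6% and 87.1%. The pattern is the same.

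**The case against.** The strongest reply is that nothing here is wrong. Unadjusted ANOVA is valid under randomisation, its standard error already allows for chance imbalance, and the sample size was set for an unadjusted comparison. Section 8.1 also calls the study preliminary and hypothesis-generating. All of that stands: no error rate or estimate is at fault without the change.

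A reader might infer that the protocol itself names pre-block strength as limiting walking. It does not. Sections 7 and 8.1 report the therapists' opinion about weakness and pain in general on POD 1. The surrounding text, on whether a lower dose preserves strength and on motor blockade with a femoral catheter, points at least partly to weakness caused by the block. That pre-block strength predicts POD 1 walking is plausible but inferred.

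A reader might also call the gain free. It is not: there is no gain up to rho of about 0.15 and less than 1 point at 0.2. There are reasons to doubt a high rho. Section 7 describes the sensor as still in development, Appendix D reports bench tests only, and clinical testing is left to a later phase. Measurement error in patients would lower rho, and surgery and analgesia come between the measurement and the walk.

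Finally, a reader might conclude that the documents rule out stratified randomisation. They describe none, but they do not say so.

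**Conclusion.** The point holds as a cheap, optional improvement in efficiency, not as a flaw. The covariate is planned for every subject, precedes randomisation and needs no new data. At 16 per group the effect on pairwise power runs from a loss of 0.9 points at rho 0 to a gain of 9.4 points at rho 0.5 (alpha 0.05), or from a loss of 1.3 to a gain of 13.2 points at 0.05/3. The gain becomes worthwhile at rho of about 0.3 or more: 2.8 points there at 0.05 and 3.6 at 0.05/3. Whether rho reaches that value cannot be settled from the documents. The case for the change therefore rests on the asymmetry: a small, bounded loss against a possible moderate gain. The figures also depend on the plan's own 15 s difference and 15 s SD, and on the assumptions listed in the working.

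**What to change.** In section 8, before unblinding, state that the primary analysis of the POD 1 10 m walk is an ANCOVA with volume group and one fixed continuous covariate: pre-block quadriceps strength of the operative leg, measured by the sensor. Take the Bonferroni-adjusted pairwise volume contrasts from this model. Replace a missing baseline value by the overall mean of that baseline, so that no patient is lost, and keep the unadjusted ANOVA as a sensitivity analysis.

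Do not put the 15-minute post-block or postoperative strength values in the primary model, since the volume may affect them. Do not leave further covariates optional (the activity score, for instance), because that undoes the pre-specification. Section 7 names the ankle or upper leg as attachment site for the two strength tests together and does not say which leg is tested; the covariate definition should settle both.

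The cost is a few sentences of SAP text and one model term, with no new data, visits or patients. The downside is one error degree of freedom and the estimation of a slope, together about 1 point of power if the covariate is not prognostic.

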4.3 Protected populations

Prisoners

Due to the complexity of state and federal requirements governing the participation of prisoners in research, patients who are prisoners will not be considered for participation in this trial. In the unlikely event that a subject becomes a prisoner while participating in this trial, study procedures will stop and the subject will be returned to the clinical mode used prior to the intervention period or, if desired, a ventilator mode requested by the clinical care team.

Pregnancy

Patients who are known to be pregnant will be excluded from participation.

5. Trial interventions

The intervention portion of this study is the randomized assignment (1:1:1) to receive 5, 10 or 20 ml of 0.5% bupivacaine, incrementally injected. All studied volumes are well within the acceptable range for SSACNB. Randomization will be accomplished using an online service (www.randomizer.org) and prefilling sealed envelopes determining each subject's intervention group. In all other aspects, the subject will receive the standard of anesthesia care appropriate for their surgery or procedure as determined by the primary anesthesia team caring for the subject.

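### If the Bonferroni family is the three pairwise volume comparisons, Shaffer's step-down test keeps the same 5% familywise error, never rejects less, and finds further true differences more often

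*Combined protocol and SAP*

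**What the plan says.** Section 5 describes "randomized assignment (1:1:1) to receive 5, 10 or 20 ml of 0.5% bupivacaine". For the analysis, section 8 states: "The primary analyses will consist of comparing the three study volumes of injection for superiority". The tests are named next: "ANOVA and two-sample t-test will be used to compare the data between the three groups or between any two individual groups". On the significance level it says "For all tests, statistical significance will be defined as a p-value less than 0.05", and the paragraph ends by stating that "Bonferroni correction will be utilized to counteract the problem of" multiple comparisons and to control the familywise error rate.

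Section 8 does not say which comparisons form the family (pairs of volumes, outcomes or time points). It gives no adjusted level, does not say whether the correction is single-step, and does not say how the overall ANOVA relates to the t-tests.

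Section 8.1 supplies the planning values: "patients are currently able to ambulate 10 meters in approximately 45 seconds on postoperative day one with 20 ml of local anesthetic"; with less local anesthetic, "this difference could approach 15 seconds"; and "We hypothesize that the standard deviation may be of similar magnitude". It calls the study preliminary and intended to generate hypotheses.

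**The concern.** The trial's purpose is to compare 5, 10 and 20 ml, so the useful result is which volumes differ, and each arm will have only about 16 to 20 evaluable patients. Bonferroni holds all three pairs at 0.05/3 even after one difference has been established. With exactly three means that protection is more than the 5% familywise limit needs. What is at stake is power for the second and third comparisons. The validity of the result is not in question.

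**Working it through.** **Inputs.** From section 8.1: 20 ml mean about 45 s, difference up to 15 s, SD about 15 s, 16 per group raised to 20 for drop-out. From section 5: allocation 1:1:1. Assumed because the plan is silent: two-sided tests, normal data, a common SD, and a family of the three pairwise t-tests on the POD 1 walk. The plan does not say how the 15 s is spread over the arms, so the mean patterns are illustrative.

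**The plan's own figure.** Normal approximation for two means at unadjusted 0.05:

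n = 2 × (1.960 + 0.842)² × (15/15)² = 15.7, so 16 per group, as stated (17 by t-test).

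At 0.05/3 = 0.0167 two-sided, z = 2.394:

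n = 2 × (2.394 + 0.842)² = 20.9, so 21 per group (23 by t-test).

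**Why Shaffer's test holds 5%.** The procedure tests the smallest p-value against 0.05/3 and, only if that is significant, tests the other two against 0.05. For three means, two true pairwise equalities imply the third. The number of true nulls is therefore three, one or none.
- Three true: any false rejection needs the smallest p ≤ 0.05/3, which has probability at most 3 × 0.05/3 = 0.05.
- One true: rejecting it needs its own p ≤ 0.05, which has probability at most 0.05.
- None true: no false rejection is possible.

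Every pair with p ≤ 0.05/3 is still rejected, so no Bonferroni finding is lost.

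**Size of the gain.** Simulation of 200,000 trials per case, SD 15 s, two-sided two-sample t-tests (simulation standard error at most 0.1 percentage point). Means are for 5/10/20 ml.

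| Means (s), n per arm | Quantity | Bonferroni | Shaffer |
|---|---|---|---|
| 30/30/45, 16 | each true difference | 62% | 70% |
| | both true differences | 46% | 63% |
| | at least one rejection | 77.6% | 77.6% |
| | false rejection, 5 v 10 ml | 1.67% | 4.88% |
| 30/30/45, 20 | each true difference | 74% | 82% |
| | both true differences | 61% | 76% |
| | at least one rejection | 87.6% | 87.6% |
| | false rejection, 5 v 10 ml | 1.68% | 4.95% |
| 30/37.5/45, 20 | each 7.5 s step | 19% | 32% |
| | 5 v 20 ml | 74% | 76% |
| | at least one rejection | 76.7% | 76.7% |
| 45/45/45, 16 | any false rejection | 4.35% | 4.35% |
| 45/45/45, 20 | any false rejection | 4.29% | 4.29% |

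The mirror pattern 30/45/45 s gives almost the same figures as 30/30/45 s.

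**How often the two procedures differ.** Shaffer's test rejected more than Bonferroni in 19.5% (n = 16) and 17.9% (n = 20) of trials with 30/30/45 s, in 21.6% and 25.3% with 30/37.5/45 s, and in about 1.2% with no difference. Not all extra rejections are true findings. With 30/30/45 s and 16 per arm, the mean number of rejections rises from 1.25 to 1.45. Of that 0.20, about 0.03 (4.88% − 1.67%) is false rejection of the equal pair, which stays within the 5% allowed.

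**The case against.** Bonferroni is valid and does what section 8 asks of it. In a preliminary, hypothesis-generating trial a conservative rule is defensible. It also gives matching simultaneous confidence intervals directly. Step-down tests have no equally simple ones, and section 8 lists confidence intervals among its summaries. The three-pair family and the single-step form are inferred. If the family also covers secondary outcomes or time points, the three-group shortcut and the power figures above do not describe the plan. All of this stands, and it limits the point to an efficiency gain on a stated assumption.

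A reader might infer more than the documents support:
- That a step-down test usually finds more. Under the effects tried, the results were identical in about 75-82% of trials.
- That it makes a positive trial more likely. Its first step is the Bonferroni threshold, so the chance of at least one finding is the same.
- That power is given up for no return. The simple matching intervals are a real, if small, return.
- That p < 0.05 for all tests contradicts the correction. Bonferroni-adjusted p-values can be compared with 0.05, so the two sentences are unclear together but not contradictory.
- That an ANOVA at 0.05 followed by unadjusted pairs is the same thing. It is also valid for three groups and slightly more powerful in the 30/30/45 s pattern (73% and 84% per difference), but it loses a finding that Bonferroni would have made in about 0.6-1.6% of simulated trials.

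**Conclusion.** The point holds as an inexpensive improvement in efficiency. For three pairwise comparisons, Shaffer's test dominates Bonferroni at the same familywise limit. The gain is about 8 percentage points per true difference and 15 to 17 points for finding both when two volumes share a mean. When the means are evenly spaced and 20 per arm are evaluable, it is about 13 points for each adjacent step and about 2 points for 5 v 20 ml. These sizes rest on SD 15 s, normal data, two-sided tests, the illustrative means and the assumed family. The dominance itself needs only the three-pair family and valid pairwise tests.

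Nothing in the plan is made invalid or biased by Bonferroni. Nor does the change mend the sample size: section 8.1 reaches 16 per group at unadjusted 0.05, and at 16 per arm Shaffer's test gives 70% per pair in the 30/30/45 s pattern, still short of 80%. That mismatch is a separate matter.

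**What to change.** For the primary endpoint, replace the Bonferroni sentence in section 8 with a definition of the family and one pre-specified procedure, for example:

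*The family for the primary endpoint is the three pairwise comparisons (5 v 10, 5 v 20 and 10 v 20 ml) of the POD 1 10 m walk. They are tested with Shaffer's step-down procedure: the smallest p-value against 0.05/3 and, if that is significant, the other two against 0.05. Significance at p < 0.05 refers to multiplicity-adjusted p-values for this family.*

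The adjusted p-value for each pair is the larger of its own p-value and three times the smallest p-value, capped at 1. If a correction is also wanted for other outcomes or time points, state it separately with its own family.

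The cost is a change of wording, with no added patients or data. The small downside is in the intervals. Bonferroni-adjusted intervals (1 − 0.05/3 = 98.3% each) can be reported alongside, with a note that they may include zero for a pair that the step-down test rejects.
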